## Protocol

Preterm infants will be recruited at gestational age 240/7-286/7 weeks GA. Each infant will be randomized to receive either the PULSED NTrainer or SHAM intervention using a software random integer function in Minitab v.17 (www.minitab.com). As shown in Figure 1, infants assigned to the PULSED NTrainer group will receive a progressive dose of the pulsatile orocutaneous stimulation. Beginning at 30 weeks' PCA, these infants will receive 2 weeks of low-dose PULSED NTrainer stimulation (2 x 3-minute blocks) with a 1-minute stimulus 'off-period' between the stimulation blocks. This form of stimulation will be given simultaneous with tube feedings 3 times/day. The stimulus dose will then be increased over the next 2 weeks (3 x 3-minute blocks of PULSED NTrainer stimulation) with a 1-minute stimulus 'off-period' between the stimulation blocks, also given simultaneously with tube feedings 3 times/day. Preterm infants randomized to the SHAM condition will be given a regular silicone pacifier during tube feedings over the same time period.

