### **NNS Assessment and Automated NNS Digital Signal Processing and Feature Extraction**

In addition to the oral stimulation interventions (PULSED NTrainer vs. SHAM pacifier), all study infants will be assessed 3 times/week (e.g., Mon/Wed/Fri) for NNS performance. The NTrainer System® will be used in 'assessment mode' to record the compression dynamics of NNS during a 3-minute session to immediately precede a tube feeding that is not associated with an intervention condition.

The most active 2-minute period of NNS behavior based on suck cycle count is automatically extracted from each suck assessment data file using an automated waveform feature extraction algorithm on the NTrainer System®. The NNS pressure waveform is band-pass filtered (0.5-20 Hz) to remove low frequency offsets due to tongue/jaw posturing and thermal drift associated with oral contact on the pacifier bulb, and to remove high-frequency jitter. Pressure peaks > 1.6 cm H2O are subjected to feature extraction criteria, including suck cycle symmetry, cycle duration, and burst identification defined as two or more NNS events occurring within 1200 ms.

This algorithm permits objective identification of NNS burst activity distinct from non-NNS mouthing compressions or tongue thrusts against the pacifier. Four measures will be objectively extracted from the indexed records of suck compression, including (1) NNS Bursts/min where an individual burst includes 2 or more suck cycles, (2) NNS Cycles/min, (3) NNS Spatiotemporal Index, and (4) NNS compression pressure (cm H2O).

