A-priori power calculation indicated that a sample size of 110 was required for 80% power, with an assumed correlation of 0.60 among repeated measures and a small effect over time (Cohen's $f = 0.10$). This effect was considerably smaller than those observed in our previous empirical data ($f = 0.22-0.24$), suggesting adequate power for the final sample of 114 neonates in this study.

Linear mixed modeling (LMM) analysis was performed for non-nutritive suck (NNS) variables including NNS Bursts/minute, NNS Suck Cycles/minute, NNS Amplitude, NNS Spatiotemporal Index, and the transition to independent oral feeds based on daily measures of percent oral intake (%PO) to examine the effects of GA, PMA, sex (male, female), respiratory diagnosis (non-BPD, BPD), treatment (NTrainer, Sham), intervention phase (0, baseline), (1, low-dose), (2, high-dose), (3, post intervention), and potential interactions. The models

accounted for nesting of repeated measurements within infants (i.e., intraclass correlation), and a proper error covariance structure was determined based on model fit (i.e., adjusted Akaike Information Criterion, Bayesian Information Criterion). In addition, locally estimated scatterplot smoothing (LOESS) analysis was conducted to estimate the trajectory of %PO growth over PMA. All statistical analyses were conducted using R [1] and SAS 9.4 [2].

References

1. R Core Team. R: A language and environment for statistical computing. R Foundation for Statistical Computing (2019) <http://www.R-project.org/>
2. SAS Institute. SAS/STAT 9.4 user's guide. (2002-2012).

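### The SAP names no infant-specific PMA slope for the NNS mixed models; if infants mature at different speeds and a simple error structure is selected, an arm-by-PMA test can reject too often

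*SAP*

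**What the plan says.** The secondary-outcome section of the SAP (Non-nutritive Suck Dynamics and Growth in Daily Oral Feeds) is the only place that specifies the mixed models. They cover four NNS variables and daily percent oral intake. Effects include GA, PMA, sex, BPD status, treatment, a four-level intervention phase, and interactions that are not listed one by one.

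On within-infant dependence, it says the models "accounted for nesting of repeated measurements within infants (i.e., intraclass correlation), and a proper error covariance structure was determined based on model fit". The selection criteria follow in brackets: "i.e., adjusted Akaike Information Criterion, Bayesian Information Criterion". It gives no random slope, candidate structures, degrees-of-freedom method or robust variance.

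The series is long. The protocol's NNS assessment section says "all study infants will be assessed 3 times/week", and treatment runs for two weeks at each of two dose levels, with baseline and post-intervention phases around it.

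For size, the SAP states "A-priori power calculation indicated that a sample size of 110 was required for 80% power", "with an assumed correlation of 0.60 among repeated measures", at Cohen's f = 0.10, and refers to a final sample of 114.

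**The concern.** An intraclass correlation describes a constant shift for each infant. If infants also differ in their rate of maturation, the variance between infants changes with PMA. Independent or AR(1) residuals around a random intercept cannot represent that. The model then counts part of the between-infant difference in growth as visit-level noise, which it averages over every session. The standard error of any contrast between arms in the rate of change comes out too small.

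AIC or BIC can select only from what is offered. If neither a random slope nor a flexible matrix is a candidate, choosing the best fit does not remove the problem.

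Arm-by-PMA is the term that would most directly show NTrainer changing the course of suck development. A false-positive rate above 5% there would bear on a main secondary conclusion.

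**Working it through.** **Inputs from the documents.** 114 infants; correlation 0.60 among repeated measures, used here as the mid-period intraclass correlation; three NNS sessions a week over four intervention weeks, so 3 × 4 = 12 visits.

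**Assumed, because not stated.** Equal arms (57 each); alpha 0.05; 18 visits once baseline and post-intervention sessions are added; a between-infant slope SD of 0, 0.3, 0.6 or 0.9 total SD over the whole period.

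**The plan's own figure.** Take the repeated-measures F test with two groups, λ = N·m·f²/(1−ρ) and df (m−1) and (N−2)(m−1). With m = 4 (assumed, matching the four phases), λ = 110 × 4 × 0.01/0.40 = 11.0. Power at N = 110 is 0.799, and 0.80 is reached at N = 111. The stated 110 is therefore reproduced under those assumptions. With m = 3, 5 or 6 the same formula gives 130, 97 or 87. This supports using 0.60 but does not otherwise bear on the covariance question.

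**Closed form, random-intercept fit.** Set total variance to 1, so residual variance s² = 0.40. Code time to run from −0.5 to 0.5 over T equally spaced visits, so Sxx = T(T+1)/[12(T−1)]. With slope variance τ², the true variance of the slope contrast is proportional to s² + τ²·Sxx. The fitted model uses s² + τ²·Sxx/(T−1). Their ratio is

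VR = (s² + τ²·Sxx) / (s² + τ²·Sxx/(T−1)).

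For T = 18 and slope SD 0.6:
- Sxx = 18 × 19/(12 × 17) = 1.676, and τ²·Sxx = 0.36 × 1.676 = 0.6035.
- VR = 1.0035/0.4355 = 2.30.
- The critical t on 112 df is 1.981, and 1.981/√2.30 = 1.305. The two-sided rejection rate is about 0.194.

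For T = 12 and the same slope SD, Sxx = 1.182, VR = 0.8255/0.4387 = 1.88 and the rate is about 0.151. Both agree with the large-sample results below (0.195 and 0.153).

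**Large-sample type I error.** No arm effect, independent residuals, REML GLS fits; the three figures are for slope SD 0.3 / 0.6 / 0.9.

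| Fitted structure | Visits | Arm-by-PMA | Arm-by-phase (arm-by-PMA not in model) |
|---|---|---|---|
| Random intercept | 12 | 0.079 / 0.153 / 0.239 | 0.060 / 0.096 / 0.145 |
| Random intercept | 18 | 0.091 / 0.195 / 0.306 | 0.068 / 0.124 / 0.199 |
| Random intercept + AR(1) | 12 | 0.072 / 0.123 / 0.170 | 0.055 / 0.068 / 0.081 |
| Random intercept + AR(1) | 18 | 0.084 / 0.165 / 0.232 | 0.061 / 0.091 / 0.120 |
| Random intercept + AR(1) + measurement error | 12 | 0.053 / 0.065 / 0.088 | 0.046 to 0.049 |
| Random intercept + AR(1) + measurement error | 18 | 0.055 / 0.072 / 0.101 | 0.046 to 0.049 |
| Toeplitz | 12 | 0.051 / 0.054 / 0.062 | 0.050 to 0.052 |
| Random intercept and slope | 12, 18 | 0.050 to 0.051 | 0.050 to 0.051 |

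At slope SD 0 every structure gives about 0.05. With arm-by-PMA also in the model, arm-by-phase is 0.017 to 0.050 under the structures without a random slope.

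**Does fit selection protect?** In simulation (12 visits, slope SD 0.6), BIC choosing among compound symmetry, AR(1) and random intercept + AR(1) gave 0.135 for arm-by-PMA and 0.095 for arm-by-phase. When a random-slope model was offered, BIC took it 98% of the time and the rates were 0.060 and 0.058. In a second simulation (400 runs, 18 visits, slope SD 0.6 and 0.9), random intercept + AR(1) + measurement error was always chosen when it was a candidate beside the two simpler structures. Arm-by-PMA error was still 0.082 and 0.138. Monte Carlo error is about 0.01 to 0.02.

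**Serially correlated residuals.** With residual AR 0.4 and slope SD 0.6, random intercept + AR(1) gives 0.085 to 0.104 for arm-by-PMA and 0.055 to 0.063 for arm-by-phase. A random slope with independent errors holds arm-by-PMA at 0.050 but puts arm-by-phase at 0.138 to 0.174, and at 0.121 to 0.170 with arm-by-PMA in the model. A slope alone is therefore not a safe repair.

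**Sandwich errors.** Infant-clustered standard errors gave 0.032 to 0.062 for both tests under every working structure tried. In the serially correlated case they gave 0.048 for arm-by-PMA and 0.032 for arm-by-phase.

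**The case against.** The strongest reply is that the SAP is silent on slopes and does not exclude them. Its error structure is open, and Toeplitz, heterogeneous-variance or unstructured matrices are all compatible with the text. A reader might infer that the models forbid an infant-specific growth rate; the document does not say so. This part of the reply stands, and the Toeplitz figures show that a flexible choice can remove most of the inflation. It is not full protection: the Toeplitz result covers 12 visits only, and an unstructured matrix over 18 visits needs 18 × 19/2 = 171 parameters from 114 infants.

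A reader might also infer that both arm-by-PMA and arm-by-phase reject at several times 5%. That is not supported. Neither interaction is named in the SAP. Arm-by-phase is near nominal under the flexible structures, and unequal slopes do not inflate it once arm-by-PMA is fitted. The slope spread behind any figure is assumed. At slope SD 0.3 the simple structures give only 0.072 to 0.091 for arm-by-PMA. If interactions of GA, sex or BPD status with PMA were fitted, they could absorb part of the spread.

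Nor does the point carry over to percent oral intake just because the same sentence covers it. In a small simulation of S-shaped daily intake, AIC chose AR(1) and error stayed at or below 5%.

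**Conclusion.** The point holds conditionally and for the NNS measures. If maturation rates differ between infants and the selected structure is a random intercept with independent or AR(1) errors, arm-by-PMA type I error is about 0.07 to 0.31 with independent residuals. With moderately autocorrelated residuals and slope SD 0.6, random intercept + AR(1) gives about 0.09 to 0.10. Without slope differences there is nothing to correct.

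This rests on an assumed slope SD of 0.3 to 0.9 total SD, 12 or 18 visits, equal arms, and an interaction inferred from the SAP's unlisted ones. The documents do not show which structure was selected, so they do not establish that any reported test was in fact inflated. The change is worth making because it is cheap and holds error near 5% where the simple structures do not. It concerns secondary analyses only.

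**What to change.** In the SAP's secondary-outcome section, for the NNS models:

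- Add an infant-level random slope for PMA, with an unstructured covariance with the random intercept.
- Keep a serial error structure among the AIC/BIC candidates alongside that slope. List the candidates and report which one was selected.
- Take the arm-by-time interaction tests (arm-by-PMA and, if fitted, arm-by-phase) from infant-clustered sandwich standard errors with a small-sample correction, whichever structure is selected.

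The SAP is written as a report of completed analyses, so this means a short rerun: one more random term and an empirical-variance option in software the SAP already lists. No new data are needed. Intervals become somewhat wider where slopes vary and change little where they do not. The percent-oral-intake models need no change on this ground.
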